Given the clinical relevance of NPS in ADRD, the equivocal results of the therapeutic resources available to address it, and the emerging evidence of safety and efficacy of tDCS in ADRD, our proposal aims to test the acceptability, safety and efficacy of home-based tDCS for the treatment of NPS in ADRD. Home-based tDCS circumvents critical problems observed in previous trials (16), including the need of multiple visits to medical centers for tDCS application, allowing a more intensive application (e.g. 5 x per week) for long periods.

Objectives

Objectives	Outcome Measures
Primary objective To assess acceptability and safety of providing tDCS to ADRD patients with behavioral symptoms.	Acceptability will be evaluated using Likert scale (from 0 [strongly disagree] to 10 [strongly agree]) to answer ten affirmatives regarding the use of home-based tDCS. Safety will be assessed with a questionnaire about side effects that include itching, burning, headache, fatigue, and dizziness. Acceptability scale will be applied on Week 2, 4, 6 and 12. Side effects questionnaire will be applied on Week 2, 4 and 6.
Secondary objectives To assess the efficacy of tDCS for ADRD on clinical outcomes, mainly behavioral symptoms.	Behavioral symptoms and cognitive measures evaluated through validated tools: NPI, bDAS, CSDD, MMSE. NPI will be applied on Baseline, Week 2, 4, 6 and 12, while bDAS, CSDD and MMSE will be applied on Baseline, Week 6 and Week 12.

Study Design

We will carry out an open-label study to evaluate home-based active tDCS for AD and behavioral symptoms. There will be no randomization. All eligible patients will receive exactly the same treatment. All participants (n=20) will receive active tDCS with a constant current intensity of 2mA. Anodal tDCS will be applied to the left dorsolateral prefrontal cortex, while cathodal electrode will be positioned on the right dorsolateral prefrontal cortex. Caregivers will help setting up and administering tDCS for participants with AD at home. tDCS will be applied for 30min at an intensity of 2mA, with

30 s ramping up and down.

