We will target the stimulation on the dorsolateral prefrontal cortex based on the facts that prior studies showed positive results with this strategy for behavioral and cognitive symptoms of other neuropsychiatric disorders (17-19). According to previous home-based tDCS protocols (20, 21), all sessions will be remotely supervised by trained research staff (RA), therefore, the sessions will run from Monday through Friday for four consecutive weeks. The remote supervision of the sessions will be possible through video conferencing software (e.g., WebEx), and will ensure the use of proper technique and compliance to the study schedule, also monitoring any adverse events. The device (tDCS) will be programmed and cannot be tampered. Participants will be assessed at baseline, treatment day 14, treatment day 28, treatment day 42- and 6-weeks post-treatment (Fig.1). The device will be delivered to patients at baseline and will be returned at the end of the treatment (week 6).

Sample size

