Safety will be assessed with a questionnaire about side effects that include itching, burning, headache, fatigue, and dizziness (21). The most common side effects of tDCS reported in the literature are very mild and include tingling, burning sensation, and skin redness, while other less common side effects may include headache, sleepiness, dizziness, and difficulty concentrating (22-23). Although rare, a possible adverse event of tDCS is the occurrence of skin lesions or small skin burns on the site where electrodes touch the skin (24-25). The side effects questionnaire will be applied on Week 2, 4 and 6 to assess the incidence and frequency of side effects in our recruited sample. We expect that the occurrence of side effects will be similar to the frequencies reported in the scientific literature, demonstrating that home-based tDCS is a safe and feasible intervention to be used on the management of ADRD patients with behavioral symptoms.

Secondary Outcome

The main efficacy measure will be change on the Neuropsychiatric Inventory (NPI) score (26), the best-validated tool for measuring NPS in dementia patients. This 12-item informant-based interview is a widely accepted measure of NPS in dementia. The NPI consists of a detailed evaluation of the following 12 neuropsychiatric domains: hallucinations, delusions, agitation/aggression, depression, anxiety, irritability, disinhibition, euphoria, apathy, aberrant motor behavior, change in night-time sleep behavior, and changes in appetite and eating (27). Each NPS domain is rated according to its severity (0-3) and frequency (0-4) (28). NPS will be assessed at baseline, during treatment (weeks 2, 4 and 6) and 6 weeks post-treatment. Our hypothesis is that patients receiving tDCS will demonstrate lower NPI scores at the end of treatment.

Other clinical outcome measures will include: (1) total score on the Brief Dimensional Apathy Scale (bDAS) (29); (2) depressive symptoms as assessed by the

Cornell Scale for Depression in Dementia (CSDD) (30); (3) cognition as evaluated by the Mini-Mental State Examination (MMSE), which includes memory, language, praxis and orientation tasks, yielding a global cognition score ranging 0 to 30, with higher scores indicating better performance (31). Our hypothesis is that all participants receiving treatment will demonstrate lower scores on the bDAS and CSDD, and higher scores on the MMSE at the end of treatment.

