NPI will be applied on Baseline, Week 2, 4, 6 and 12, while bDAS, CSDD and MMSE will be applied on Baseline, Week 6 and Week 12.

Sociodemographic and Clinical (health history, use of medication and life habits) *data* (gender, age, marital status and education) will be collected at the baseline.

Assessment	Baseline	Week 2	Week 4	Week 6	Week 12
Medical History Questionnaire	X				
MMSE (Secondary outcome)	X			X	X
NPI (Secondary outcome)	X	X	X	X	X
bDAS (Secondary outcome)	X			X	X
CSDD (Secondary outcome)	X			X	X
tDCS experience questionnaire (Primary outcome)		X	X	X	X
Side effects questionnaire (Primary outcome)		X	X	X	

Table 1. Timetable for Collection of Data

Data and Safety Monitoring

Data will be collected from 20 human participants, and all information will be de-identified in order to protect their confidentiality. All clinical information will be stored in dedicated files at UT Health Department of Psychiatry and Behavioral Sciences. The data generated in this project will be presented at national or international conferences and published in a timely fashion.

Statistics

Statistical modeling will primarily use generalized linear modeling (GLM) with multilevel components (GLMM) for correlated observations. Potentially nonlinear relationships between predictors and outcomes will be evaluated via inclusion of polynomial or spline effects. Continuous, dichotomous, and count-distributed data will utilize linear, logistic, and Poisson/negative binomial regression, respectively (each with a canonical link function). Evaluation of distributional assumptions will use residual plots, formal statistical tests, and posterior predictive checking. Violations of assumptions will be addressed via transformation, robust estimation, stratification, and/or coefficient scaling

where appropriate. Statistical analyses will be performed using the R statistical computing environment via packages lme, rstan, and brms.

Ethics/Protection of Patient Confidentiality

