Potential Benefits to Research Participants. If our hypothesis is correct, all subjects might benefit from the study participation. Importantly, the results will be relevant to the field of AD and neuromodulation.

Significance

Our proposal will address a frequent and sometimes overlooked clinical problem in patients with ADRD, i.e. behavioral symptoms. The proposal can advance the field of non-pharmacological strategies for NPS, also presenting a great potential for clinical translation. Home-based intervention with real-time monitoring through a secure conferencing platform is a new modality for improving symptom management in ADRD. Moreover, home-based, remotely supervised tDCS has advantages over clinic-based sessions, considering the time and cost associated with attending multiple sessions over several days. Caregivers will be trained at the in-person baseline visit, and all the tDCS sessions will be remotely supervised via secure videoconferencing software by trained research staff for the entire duration of each session to ensure the use of proper technique and to monitor any adverse events.

Costs and Compensations

Participants will not be charged for tests, procedures or other costs incurred solely for the purposes of this research. Patients will receive a voucher of US 50.00 for their time dedicated to each evaluation (total number of assessments = 5).

Publication Plan

This study will represent an original contribution to the areas of non-pharmacological approaches for NPS in ADRD and neuromodulation. The results will be presented in national and international meetings, and published as a research manuscript.

References

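### Adverse events that staff see in supervised sessions have no stated path into the primary safety result, which rests on a questionnaire given at three visits

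*Combined protocol and SAP*

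**What the plan says.** The Objectives table gives the primary aim as follows: "To assess acceptability and safety of providing tDCS to ADRD patients with behavioral symptoms". Under Study Procedures, Primary Outcome, the safety paragraph opens: "Safety will be assessed with a questionnaire about side effects that include itching, burning, headache, fatigue, and dizziness". It then gives timing and purpose: "The side effects questionnaire will be applied on Week 2, 4 and 6 to assess the incidence and frequency of side effects in our recruited" (the quoted sentence is cut one word short). Table 1 agrees, marking the form at Weeks 2, 4 and 6 as a primary outcome. It has no row for adverse events.

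The same safety paragraph lists tingling and skin redness among the most common effects of tDCS. It also names a rarer harm: "the occurrence of skin lesions or small skin burns on the site where electrodes touch the skin". The risk text under Ethics repeats that harm.

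Supervision is described twice. Study Design says that remote supervision by video "will ensure the use of proper technique and compliance to the study schedule, also monitoring any adverse events". Significance says that staff supervise "for the entire duration of each session to ensure the use of proper technique and to monitor any adverse events".

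The Data and Safety Monitoring section has three sentences. The first says that "all information will be de-identified in order to protect their confidentiality", the second concerns file storage, and the third concerns presentation and publication. The Statistics section describes regression models by outcome type and names no adverse event analysis.

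**The concern.** The trial has a trained observer at every session and safety in its primary objective, but the plan does not connect the two. Adverse events are to be monitored. No section says that they are logged, graded, reported or added to the safety result. The section whose title promises safety monitoring contains none.

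The questionnaire is meant to yield incidence and frequency. The investigators expect frequencies like those in the literature and would read that as showing home treatment to be safe and feasible. If events seen by staff are left out, the omission favours the expected conclusion. In a single-arm study of 20 people, one or two omitted events visibly change the reported rate.

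**Working it through.** The plan states no figure for safety, so there is none to reproduce. Its only power figure (80% at d = 0.66, N = 20) concerns change in efficacy measures. It reproduces at 79.9% with a two-sided paired-change t-test and does not bear on this point. The check is mainly textual, with a little arithmetic for scale.

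**1. Follow one event through the plan.** Suppose staff see a skin reaction in a session.
- Study Design and Significance: staff are monitoring, so they notice it.
- Table 1: no adverse event form or row exists on which to enter it.
- Data and Safety Monitoring: no recording, grading, review or reporting step.
- Primary Outcome (safety): the result is built from the questionnaire.
- Statistics: no analysis of adverse events from any other source.

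The only stated way in is for someone to report the event again at the next questionnaire.

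**2. Compare the named harms with the named items.** The plan names five symptoms for the questionnaire. Tingling, skin redness and skin lesions or burns appear in the same safety paragraph but not among those five. Burning is listed, but the Ethics text treats it as a scalp sensation, which is not the same as a lesion. The list is open-ended and the form is not reproduced, so these items are not stated rather than shown to be absent.

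**3. Count the observation points.** Inputs: 20 participants (Study Population), 3 forms each (Table 1), 5 sessions a week for six weeks (General Information) or on weekdays for four weeks (Study Design).
- Scheduled safety forms: 20 × 3 = 60.
- Sessions, six-week text: 5 × 6 = 30 per participant; 30 × 20 = 600.
- Sessions, four-week text: 5 × 4 = 20 per participant; 20 × 20 = 400.

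The two texts contradict each other, and any per-session rate needs one denominator.

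**4. What one missed event does with N = 20.** Exact (Clopper-Pearson) 95% limits:
- 0/20: lower limit 0; upper limit 1 − 0.025^(1/20) = 0.168. Interval 0 to 16.8%.
- 1/20 = 5%: lower limit 1 − 0.975^(1/20) = 0.0013; upper limit, the 97.5% point of Beta(2, 19), = 0.249. Interval 0.1% to 24.9%.

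**5. How likely there is an event to miss.** The documents call skin lesions rare and give no rate. Assuming independent participants with per-participant risk p, the chance of at least one affected among 20 is 1 − (1 − p)^20:

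| Assumed p | Chance of at least one in 20 |
|---|---|
| 1% | 18% |
| 2% | 33% |
| 5% | 64% |
| 10% | 88% |

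These values of p are assumptions. The table shows whether an event would occur, not whether it would be missed.

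**The case against.** The best defence is that a published side-effects questionnaire, repeated three times, is a reasonable measure for a small descriptive single-arm study. The caregiver must be present at sessions and at assessments, under Ethics expressly so that information is reliable. A burn seen in a session can therefore be reported by that caregiver on the next form, and the open list has a burning item. This stands as mitigation. It makes it too strong to say that such events have no way in at all. It does not supply a step that records what staff see, or a rule that counts it.

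Three stronger readings are tempting and are not supported.
- **The form omits skin lesions, tingling and redness.** The questionnaire is cited, not reproduced, and the list is open. They may be on it.
- **Rates are biased low because people with dementia must recall two weeks of sessions.** The documents give neither the recall window nor the respondent for the safety form. The wording that allows participants or caretakers to answer belongs to the acceptability scale. The caregiver's presence also weakens the argument.
- **The under-count can be put as a percentage from an assumed per-session rate.** That needs a rate which the documents do not give, independence between sessions within a person, and no recall between forms. If effects cluster in the same people, the gap shrinks or disappears. Under the four-week text the Week 6 form also falls about two weeks after the last session, so three forms cannot be treated as three fresh observations.

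It can also be said that a per-session checklist is a matter of preference. A narrower repair would log in-session events and summarise them beside the questionnaire. That would close the recording gap but leave the primary safety result able to exclude a known event.

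**Conclusion.** The point holds as a gap between what is observed and what is counted. Safety is a primary outcome with one stated measure, every session is watched, and the plan followed as written can leave an event seen by staff out of the primary result. This is more than missing detail, because it determines what the reported incidence means.

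The conclusion is that side effects may be under-counted. The documents do not show that they will be, or by how much. That depends on an unseen form, an unstated respondent and recall window, and how often caregivers repeat what staff saw. The size that can be given is the scale: 60 forms against 400 or 600 sessions, and an estimate that moves from 0% to 5%, with the upper limit going from 16.8% to 24.9%, on a single event. The finding rests on the text and does not depend on the assumed risks shown above. The change is worth making because the outcome is primary and the remedy is cheap.

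**What to change.** - Have the supervising staff complete a short side-effect checklist at the end of each session, with skin reaction, tingling and redness as explicit items.
- Keep the questionnaire at Weeks 2, 4 and 6.
- Define the primary safety summary as the number and proportion of participants with any side effect or adverse event from session records, questionnaires or spontaneous report, with exact 95% confidence intervals. Add a per-session rate and list serious events separately.
- State in Data and Safety Monitoring how events are recorded and who reviews and reports them.
- Reconcile the four-week text in Study Design with the six-week text in General Information, so that the per-session denominator is fixed.

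The cost is a few minutes of staff time per session, from people already present, and some added wording in the safety, monitoring and statistics sections. No extra visit or participant is needed and treatment is unaffected. Reported rates will probably be higher than from the questionnaire alone. The report should say so when setting them against literature figures that may have been collected differently.

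### The primary side-effects questionnaire has no baseline administration, so headache, fatigue or dizziness present before treatment may be counted in the reported incidence

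*Combined protocol and SAP*

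**What the plan says.** The Primary Outcome section under Study Procedures defines the measure: "Safety will be assessed with a questionnaire about side effects that include itching, burning, headache, fatigue, and dizziness". It then sets the schedule and purpose: "The side effects questionnaire will be applied on Week 2, 4 and 6 to assess the incidence and frequency of side effects". The Objectives table repeats the weeks ("Side effects questionnaire will be applied on Week 2, 4 and 6"). The Table 1 row "Side effects questionnaire (Primary outcome)" has three marks, read as Weeks 2, 4 and 6. The three places agree, so this is the intended schedule.

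The Study Design section rules out a comparator: "There will be no randomization. All eligible patients will receive exactly the same treatment". The baseline clinical data are described as "health history, use of medication and life habits". Nothing says that they cover the questionnaire's items or enter the side-effect analysis. Study Design and Significance provide for live remote supervision of every session, with monitoring for adverse events, but give no causality or grading rule.

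On interpretation, the Primary Outcome section says "We expect that the occurrence of side effects will be similar to the frequencies reported in the scientific literature". The same sentence treats such a result as "demonstrating that home-based tDCS is a safe and feasible intervention". No reference rate, margin or threshold is given.

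**The concern.** Incidence means new occurrence. Three of the five named symptoms (headache, fatigue and dizziness) are non-specific and can be present in older people with dementia before any stimulation. With no pre-treatment value and no untreated group, a standing symptom reported at Week 2 may enter a primary outcome as a side effect. Itching and burning under the electrodes are less exposed.

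The likely direction is an overstated rate, so that tDCS looks less safe than it is, and the planned data would not show by how much. Comparison with published rates does not settle this: those rates may carry the same background, so the direction of error in that comparison is unknown.

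A smaller matter works the other way. If the result is favourable, the plan's wording would describe 20 participants as demonstrating safety.

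**Working it through.** **The plan's own figure.** The Sample size section gives 80% power at N = 20, alpha 0.05, d = 0.66. A two-sided paired t-test (19 degrees of freedom, noncentrality 0.66 × √20) gives 79.9%, so the figure reproduces. It concerns change from baseline and has no bearing on side-effect rates, for which the plan gives no figure.

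**Effect of the missing baseline.** From the plan: N = 20, one arm. Assumed, because the documents give no values:
- q, the true tDCS-related rate for one symptom, 10%
- p, the share of participants with the symptom before treatment and persisting, 5% to 30%
- r, the share of those pre-existing symptoms that get reported on the form, 0 to 1
- independence of the pre-existing and tDCS-related symptoms.

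Apparent rate = rp + q − rpq. Excess participants = 20 × rp(1 − q).

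| r | Apparent rate, p = 5% / 10% / 20% / 30% | Excess of 20, p = 5% to 30% |
|---|---|---|
| 0 | 10% throughout | 0 |
| 0.25 | 11.1 / 12.25 / 14.5 / 16.75% | 0.2 to 1.4 |
| 0.5 | 12.25 / 14.5 / 19 / 23.5% | 0.5 to 2.7 |
| 1 | 14.5 / 19 / 28 / 37% | 0.9 to 5.4 |

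Example: r = 1, p = 0.30 gives 0.30 + 0.10 − 0.03 = 0.37, and 20 × 0.30 × 0.90 = 5.4. Changing q moves the top value little. At r = 1 and p = 0.30, q = 5% gives 33.5%, an excess of 20 × 0.285 = 5.7; q = 20% gives 44%, an excess of 20 × 0.24 = 4.8.

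**What 20 participants can exclude.** The exact two-sided 95% upper limit for 0/20 is 1 − 0.025^(1/20) = 16.8%. The exact interval for 2/20 is 1.2% to 31.7%. The Sample size section makes Bayesian inference primary, so the posterior counterpart for 0/20 is also relevant. The 97.5th percentile is 16.1% with a uniform prior, Beta(1, 21), and 11.7% with a Jeffreys prior, Beta(0.5, 20.5). If the true rate were 5%, the chance of seeing no case would be 0.95^20 = 36%.

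**Denominator if only presence is recorded.** Participants with the symptom at baseline could then not show a new onset. With 5% to 30% affected, 19 to 14 participants remain, and the limit for zero events, 1 − 0.025^(1/n), rises to 17.6% to 23.2%.

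**The case against.** The strongest objection is that the form has not been seen. It is taken from a cited trial of home-based tDCS in knee osteoarthritis and is called a side-effects questionnaire, so it may already ask whether a symptom began with, or is related to, stimulation. In that case r is near zero and the problem largely disappears. This stands, and it limits the claim. A reader might infer that prior symptoms cannot be separated from tDCS effects at all; the documents do not support that, because they do not print the form.

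Staff also watch every session and monitor adverse events, caregivers attend, and health history is taken at baseline. These could show that a symptom came before stimulation. That is real but partial mitigation: the information is unstructured, and no section links it to the questionnaire outcome.

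The size in the table rests wholly on assumed rates and runs from nothing to about 5 of 20. That is fair; it shows what could happen and estimates nothing.

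A baseline form does not establish causation in a single arm. This is also true. It removes only the component already present at baseline.

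On wording, the safety sentence is an expectation, the stated aim is descriptive, and zero events is not what the plan predicts. A reader might infer that a formal safety conclusion is to be tested. None is planned, so this remains a wording matter. Nor does a limit of 16.8% for a mild symptom such as itching contradict safety; the limit weighs more for serious events.

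**Conclusion.** The point holds in a conditional form. The missing baseline, the single arm and the absence of an attribution rule are plain in the text. Whether they bias the reported incidence depends on the form's wording. If the form does not ask about onset or relation to stimulation, the rates for headache, fatigue and dizziness may be overstated. The amount is unknown: 0 to about 5 of 20 participants per symptom under the assumed rates.

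This is a design gap and not a contradiction. The mentions of sham sessions and of groups in the recruitment and acceptability text might suggest a control arm, but Study Design says everyone receives the same treatment.

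The change is worth making because it is cheap and bears on a primary outcome. The wording on demonstrating safety is secondary; it rests only on N = 20 and the limits above.

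**What to change.** Add a Baseline mark in Table 1 for the same symptom items, given before the first session. Word it as a symptom checklist, since a form about tDCS side effects may not work unchanged before any tDCS. Include a severity grade if the form does not already have one, so that worsening can be counted and the loss of denominator is avoided.

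For each item, report two proportions, each with a 95% interval: the raw proportion with the symptom during treatment, which keeps the comparison with published rates, and the proportion with a new or worsened symptom relative to baseline. A posterior interval with its prior stated would match the plan's primary inference; an exact interval also serves. For participants already treated without a baseline form, report the limitation.

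Replace the wording about demonstrating safety with a descriptive statement that gives the interval.

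The cost is about 20 extra forms (4 × 20 = 80 scheduled instead of 3 × 20 = 60) at the existing in-person baseline visit, minor rewording of the form and a more modest safety statement. The new-or-worsened rate may not be directly comparable with published rates, and background symptoms that start after baseline will still be counted.
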